9.3 Variables

9.3.1 General considerations for data collection

With respect to the observational or non-interventional nature of the PASS, only examinations may be recorded if they are part of the routine assessment of the patients. No examinations should be conducted for the purpose of completing this protocol alone, as this would change the study to interventional.

However every effort should be made to carefully collect and record all available data for safety, treatment, and treatment outcome of the individual patient enrolled in this PASS, and to complete the case report form (CRF) as comprehensive as possible.

9.3.2 Baseline disease characteristics and demographics

Unless otherwise stated, *baseline* is defined as the first observation at the time the patient is included in the registry. The following information will be collected at baseline:

- 1. Patient age, gender and race
- 2. MF diagnosis (major and minor criteria which qualified the patient for diagnosis of MF)
- 3. Date of first diagnosis of MF
- 4. MF current risk group (DIPSS risk category for patients previously diagnosed and IPSS risk category for newly-diagnosed)
- 5. JAK2V617F mutation status
- 6. Spleen Length
- 7. Constitutional Symptoms
- 8. Body weight
- 9. Prior transfusional history (PRBC's and platelets)
- 10. Date and results of bone-marrow biopsies (including fibrosis score and staining methodology)
- 11. Prior treatments of MF, including dose, dates and duration (whichever data are available), including interventions such as splenectomy or irradiation therapy
- 12. Co-morbidities, including organ impairments and previous infections
- 13. Prior history of malignancies with date of first diagnosis, pathology, treatments and current state

9.3.3 Management of myelofibrosis and co-morbidities

During the observation period the following information on the management of MF will be collected:

- 1. Medications for treatment and management of MF (e.g. ruxolitinib, HU, IMIDs, Peg Interferon, Danazol, ESA) with start date, stop date, dose and dose change, and reason for dose change or discontinuation, as appropriate
- 2. Non-pharmacologic treatments for MF (splenic irradiation, splenectomy, BMT) including dates, morbidities, duration of response and outcome
- 3. Medications for MF symptoms, with start and stop date, dose and indication
- 4. Use of blood or platelet transfusions
- 5. Medications for the management of co-morbidities, with start and stop date, dose and indication
- 6. Subsequent bone marrow biopsies as clinically indicated during standard clinical care, reporting fibrosis scores and blast percentage
- 7. Spleen length
- 8. Constitutional symptoms
- 9. Body weight
- 10. JAK2V617F allele burden measurements, chromosomal abnormalities

9.3.4 Laboratory evaluations

At baseline and during the observation period laboratory data will be collected and recorded by their respective CTCAE category Version 4 grades:

- 1. Hematology
- 2. Clinical chemistry

Other relevant laboratory abnormalities that represent an Adverse Reaction an Event of Special Interest or a Serious Adverse Event will be collected. This includes laboratory values that are required for the interpretation of Adverse Reactions. Events of Special Interest and Serious Adverse events.

9.3.5 Treatment discontinuation

Reason(s) of discontinuation of patients from the non-interventional study will be collected:

- Subject withdrew consent
- Lost to follow-up
- Administrative problems
- Death

9.4 Data sources

The data for this study will be retrieved from the Oracle Clinical/Remote Data Capture 4.6.2 provided by Novartis or designee. A designated contract research organization (CRO) will perform the analysis following their own internal standard operating procedures (SOPs) that have been reviewed and approved by Novartis.

Initiation of the participating sites will be performed by Novartis and/or a designated CRO. Before study initiation, a Novartis representative (or designee) will review the protocol and CRF with the physicians and their staff.

Sites enrolling patients in this study will record data on eCRFs provided by Novartis (or designee) which will capture, check, store and analyze the data.

CROs will follow their own internal SOPs that have been reviewed and approved by Novartis.

Concomitant or prior medications entered into the database will be coded using the World Health Organization (WHO) Drug Reference List. Medical history/current medical conditions and adverse events will be coded using the Medical dictionary for regulatory activities (MedDRA) terminology.

Safety data will be transferred to Novartis at a frequency as defined in the protocol. Clinical data will be transferred to Novartis after closure of the study.

Data collection schedule

This is a non-interventional study and does not impose a therapy protocol, diagnostic/therapeutic procedure, or a visit schedule. Patients will be treated according to the local prescribing information and routine medical practice in terms of visit frequency and types of assessments performed and only these data will be collected as part of the study. The treating physician is asked to complete if possible at every patient visit the appropriate CRF.

However, the recommended data collection schedule that most likely mirrors the patterns of routine clinical care of most patients being treated with ruxolitinib is at 3-monthly intervals.

For patients who discontinue prematurely, the reason for discontinuation should be determined.

9.5 Study size

The study is planned to recruit patients diagnosed with MF exposed and non-exposed to ruxolitinib with the objective of enrolling at least 300 patients exposed to ruxolitinib within 2 years. It is expected that about 150 patients not exposed to ruxolitinib will be recruited during the enrolment period.

9.6 Data management

9.6.1 Monitoring Procedures

Before study initiation the sponsor personnel or a designated representative will review the protocol and corresponding documents with the investigators and their staff. During this study a field monitor may visit the site to check the completeness of patient records, the accuracy of entries in the database, the adherence to the protocol and to GCP. Key study personnel must be available to assist the field monitor during these visits. The investigator must give the monitor access to relevant hospital or clinical records, to confirm their consistency with the entries in the database. No information in these records about the identity of the subjects will leave the study center. Novartis monitoring standards require full verification for the presence of informed consent, adherence to the inclusion/exclusion criteria, documentation of serious adverse events and the recording of primary variables if available. Additional checks of the consistency of the source data with the data entered in the database are performed according to the study-specific monitoring plan.

9.6.2 Data collection

The investigator must complete the data entry forms in the database. All entries to the data forms must be made as described in completion guidelines or as instructed by the sponsor personnel or the designated representative at study initiation. Data on subjects collected during the trial will be documented in an anonymous fashion and the subject will only be identified by the subject number. If, as an exception, it is necessary for safety or regulatory reasons to identify the subject, both the sponsor and the investigator are bound to keep this information confidential. The investigator must maintain source documents for each patient in this study, consisting of all demographic and medical information, including laboratory data, electrocardiograms, etc., and keep a copy of the signed informed consent form. All information on data report forms must be traceable to these source documents in the patient's file. Data without a written or electronic record will be defined before trial start and will be recorded directly on the data report forms, which will be documented as being the source data. Essential documents, as listed below, must be retained by the investigator for as long as needed to comply with national and international regulations (generally 2 years after discontinuing clinical development or after the last marketing approval). Novartis will notify the investigator(s)/institution(s) when the study-related records are no longer required. The investigator agrees to adhere to the document retention procedures by signing the protocol. Essential documents include:

Page 23

- IRB/IEC approvals for the study protocol and all amendments
- all source documents and laboratory records •
- CRF copies (paper copies or electronic copies on a CD-ROM, depending on the study) •
- patients informed consent forms (with study number and title of study)
- any other pertinent study document.

9.6.3 Database management and quality control

Sponsor personnel or a designated representative will review the data entered by investigational staff for completeness and accuracy. When the data collection process is complete for a patient or at specified time points and the data have been validated, the data will be moved to the analysis data set.

Concomitant medications entered into the database will be coded using the World Health Organization (WHO) Drug Reference List, which employs the Anatomical Therapeutic Chemical (ATC) classification system. Medical history/current medical conditions and adverse events will be coded using the Medical dictionary for regulatory activities (MedDRA) terminology.

At the completion of entering data for a patient, the investigator must "electronically certify" or validate that the data for this patient are complete and accurate. At this point, the system will require the investigator to re-enter his password. When the database has been declared to be complete and accurate, the database will be locked.

9.7 Data analysis

All analysis will be performed by Novartis or a designated CRO.

9.7.1 Analysis sets

Full analysis set (FAS): consists of all patients who enroll into the non-interventional study.

Safety set: consists of all patients who had at least one post-baseline safety assessment and were exposed to at least one dose of ruxolitinib. Note that the statement that a patient had no adverse events (on the Adverse Event CRF) constitutes a safety assessment.

9.7.2 Patient demographics/other baseline characteristics

Demographic and other baseline characteristics including medical history and prior treatment will be summarized descriptively. Categorical data will be summarized by frequency and percentages. Quantitative data will be summarized by the number of patients (n), mean, standard deviation, median, minimum, maximum.

Data will be summarized descriptively and separately for patients exposed and non-exposed to ruxolitinib.

9.7.3 Treatments

Information about ruxolitinib treatment including daily dose, interruptions, and duration of exposure will be summarized by descriptive statistics and corresponding listing will be presented. Treatment with ruxolitinib will be at the discretion of the investigator in accordance with the prescribing information.

Other medications administered for myelofibrosis will be captured and summarized.

9.7.4 Primary objective

The primary objective of this non-interventional study is to document long-term safety in patients with myelofibrosis prescribed ruxolitinib according to the prescribing information.

Data will be summarized descriptively and separately for patients exposed and non-exposed to ruxolitinib.

The incidence of on-treatment Adverse Drug Reactions and SAEs will be summarized by system organ class and preferred term using the MedDRA dictionary. Similar summaries will also be produced for treatment-related SAEs. These listings will cover both events that occur during the on-treatment and post-treatment period however, events that occur during the post- treatment period will be flagged. All ADR and SAE data will be analyzed according to the specifications of the ruxolitinib risk management plan.

9.7.5 Secondary objectives

To document the management of patients with MF.

To document the incidence and outcome of events of special interest.

9.7.6 Interim analyses

No formal interim analyses will be performed. However, descriptive summaries will be prepared annually, for the purposes of reporting Health Authorities.

9.7.7 Sample size and power considerations

A total of approximately 300 MF patients exposed to ruxolitinib are planned for this study. It is expected that about 150 patients not exposed to ruxolitinib will be recruited.

With 300 ruxolitinib exposed patients, there is 95% probability that at least 1 patient will experience an adverse event that has a true probability of occurrence of 1%.

Furthermore, 300 patients exposed to ruxolitinib will provide enough precision to ensure the margin of error on a 95% confidence interval for estimating the rate of specific AEs of interest (herpes zoster, UTI, tuberculosis, bleeding, and intracranial hemorrhage) is less than 5%, assuming the observed rate is similar to what was observed in the COMFORT studies, which was as follows: herpes zoster: 6.5%, UTI: 10.4%, tuberculosis: 0.5%, bleeding (grade 3/4): 4.8%, and intracranial hemorrhage: 4.6%. In addition, 300 patients will provide sufficient probability (>98%) to ensure that the specific AEs of interest of will be observed to occur at least as frequently as what was seen in the pivotal trials assuming the various true occurrence rates as displayed in Table 9-1.

Table 9-1Probability to observe rates similar to COMFORT studies for specific
AEs of interest

AE	Observed rate in Comfort studies	Assumed true rate*	Probability of observing rate at least as high as in Comfort studies			
Herpes zoster	0.065	0.13	>0.99			
UTI	0.104	0.20	>0.99			
Tuberculosis	0.005	0.02	0.98			
Bleeding (grade 3/4)	0.048	0.10	>0.99			
Intracranial hemorrhage	0.046	0.10	>0.99			
* Approximately double observed rate, except for Tuberculosis, which is approximately 4 times observed rate						

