In the US, ruxolitinib was first licensed and marketed in 2011 indicated for treatment of patients with intermediate or high-risk myelofibrosis, including primary myelofibrosis, post-polycythemia vera myelofibrosis and post-essential thrombocythemia myelofibrosis. At the time point of submission of the Marketing Authorization Application in the EU, a total of 589 MF patients were exposed to ruxolitinib phase 3 studies, which was equivalent to 622 patient years of exposure. Although the number of patients exposed in clinical studies is significant considering orphan status of MF, the experience is limited by the absence of post marketing exposure including data on long term use and the typical restrictions imposed by inclusion and exclusion criteria in clinical studies. This study will provide real-world data on MF patients exposed and non-exposed to ruxolitinib and will therefore provide insights into disease management as well as the safety profile of ruxolitinib.

8 Research question and objectives

This is a Post Authorization Safety Study according to the EU Volume 9a of the Rules Governing Medicinal Products in the European Union.

Primary objective

The primary objective of this Post Authorization Safety Study is to document long-term safety in patients with myelofibrosis prescribed ruxolitinib according to the prescribing information.

[figure not shown]
Secondary objectives

- 1. To document the treatment of patients with MF including pharmacological and nonpharmacological management.
- 2. To document the incidence and outcome of events of special interest including the following:
 - bleeding events
 - serious & opportunistic infections
 - secondary malignancies
 - ADRs/ SAEs after discontinuation of ruxolitinib treatment
 - pregnancies
 - deaths of any cause

9 Research methods

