9.1.2 Discussion of study design and feasibility

To date, no large prospective observational studies have been reported that provide insight into current treatment patterns or detailed information on disease associated conditions and outcomes.

The chosen design will allow collection of data on all patients with a confirmed diagnosis of MF, irrespective of treatment modalities employed, disease severity, age, concurrent conditions or other factors that are typically controlled in interventional settings by inclusion-or exclusion criteria. Data on drug exposure including ruxolitinib, the emergence and management of events of special interest, the use of combination drug therapies, and the outcome of pregnancies will be made available. In addition, the non-interventional study logistics allow the collection and transmission of SAE and ADR data collected for patients exposed to ruxolitinib.

Ruxolitinib as an innovative treatment is intended for the long term treatment of MF. The design and logistics of the non-interventional study will allow a follow-up of "real-world" patients for 3 to 5 years. This is significantly longer than exposure experience from ruxolitinib clinical studies in MF patients. Furthermore, the disease registry will allow the continued follow-up of patients independent of exposure to certain drugs. The study will collect data from several European countries. This may balance for local treatment patterns.

There are several limitations to the study: a direct comparison or hypothesis testing between patients exposed to ruxolitinib and those who are not will not be possible due to confounding factors; i.e., patients with few manifestations of MF are expected to be managed differently from those with a more serious manifestations such as massive splenomegaly and pronounced disease symptoms. Still, data received on non-exposed patients will provide valuable context information that support the interpretation of observations made. Potential or identified risks related to ruxolitinib drug treatment have been characterized and quantified in (interventional) phase III clinical studies and therefore represent an important reference. It will therefore be possible to review solicited safety observations from this non-interventional study in the context of the safety profile of ruxolitinib established from MF clinical studies.

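### Section 9.7.7 takes COMFORT event percentages with no time basis or named source population as its reference, although this study follows patients far longer than the phase 3 exposure

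*Protocol*

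**What the plan says.** Section 9.7.7 states that 300 exposed patients "will provide enough precision to ensure the margin of error on a 95% confidence interval for estimating the rate of specific AEs of interest" stays under 5%, "assuming the observed rate is similar to what was observed in the COMFORT studies". It then lists five COMFORT figures: herpes zoster 6.5%, UTI 10.4%, tuberculosis 0.5%, grade 3/4 bleeding 4.8% and intracranial hemorrhage 4.6%. Table 9-1 uses these as thresholds and sets assumed true rates of 13%, 20%, 2%, 10% and 10%. Its footnote describes these as about double the observed rate, or about four times for tuberculosis. No follow-up time, patient-years or source population accompanies any of them.

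Section 7 gives the only exposure figure: "a total of 589 MF patients were exposed to ruxolitinib phase 3 studies, which was equivalent to 622 patient years of exposure".

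Section 9.1.2 plans 3 to 5 years of follow-up and says of it: "This is significantly longer than exposure experience from ruxolitinib clinical studies in MF patients". The same section excludes direct comparison or hypothesis testing between exposed and non-exposed patients. It calls the phase III results an important reference and expects this study's safety observations to be reviewed in that context.

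For the primary objective, section 9.7.4 says: "The incidence of on-treatment Adverse Drug Reactions and SAEs will be summarized by system organ class and preferred term". It does not say whether incidence means a proportion of patients or a rate per patient-year. Section 11.2 collects ADRs from first exposure until 28 days after discontinuation.

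**The concern.** The proportion of patients who have had an event rises with time at risk. A percentage accumulated over about one year cannot be set beside one accumulated over several years without a common time basis. The protocol knows that the durations differ, since section 9.1.2 presents the longer follow-up as a strength, yet section 9.7.7 carries the percentages across as though duration did not matter. Section 9.9 lists no limitation.

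What is at stake is how the main safety result is read. If crude percentages from this study are placed beside the COMFORT figures, a higher percentage may reflect only longer observation, and short exposure in patients who stop early could mask a real increase. Section 9.7.6 plans annual descriptive summaries for health authorities, so a cumulative percentage would tend to climb each year against a fixed figure.

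**Working it through.** **Inputs.** n = 300, the five COMFORT percentages p and the Table 9-1 assumed rates (section 9.7.7); 589 patients and 622 patient-years (section 7); follow-up of 3 to 5 years (section 9.1.2). The protocol gives no ruxolitinib discontinuation rate, so d = 0 to 0.7 per year is assumed to show a range.

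**1. The plan's own figures reproduce.**
- Probability of at least one event at a true 1%: 1 − 0.99^300 = 0.951 (stated: 95%).
- Margin of error, 1.96 × √(p(1−p)/300): zoster 2.79, UTI 3.45, tuberculosis 0.80, bleeding 2.42, intracranial hemorrhage 2.37 points. All are below 5.
- Table 9-1, binomial probability of an observed rate at or above COMFORT given the assumed true rate: 0.9999, >0.9999, 0.983, 0.9994, 0.9998. These agree with the table.
- Margin at the Table 9-1 assumed rates: the largest is UTI, 1.96 × √(0.2 × 0.8/300) = 4.53 points, still below 5.

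**2. Same hazard, longer exposure.** Mean phase 3 exposure is 622/589 = 1.056 years. With a constant hazard, h = −ln(1−p)/1.056. The cumulative proportion after T years on drug is 1 − exp(−hT). The time to reach an assumed rate a is −ln(1−a)/h.

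| Event | COMFORT % | h per 100 patient-years | Years to Table 9-1 rate | 3 years: % (ratio) | 5 years: % (ratio) |
|---|---|---|---|---|---|
| Zoster | 6.5 | 6.36 | 2.19 | 17.4 (2.67) | 27.3 (4.19) |
| UTI | 10.4 | 10.40 | 2.15 | 26.8 (2.58) | 40.5 (3.90) |
| Tuberculosis | 0.5 | 0.47 | 4.26 | 1.4 (2.83) | 2.3 (4.69) |
| Bleeding gr 3/4 | 4.8 | 4.66 | 2.26 | 13.0 (2.72) | 20.8 (4.33) |
| Intracranial hem. | 4.6 | 4.46 | 2.36 | 12.5 (2.72) | 20.0 (4.34) |

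**3. Allowing for discontinuation.** With exponential discontinuation at rate d, the proportion with an on-drug event by T is h/(h+d) × (1 − exp(−(h+d)T)). Ratio to COMFORT across the five events:

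| d per year (assumed) | 3 years | 5 years |
|---|---|---|
| 0 | 2.6–2.8 | 3.9–4.7 |
| 0.1 | 2.2–2.4 | 3.1–3.7 |
| 0.2 | 2.0–2.1 | 2.6–3.0 |
| 0.3 | 1.7–1.9 | 2.2–2.4 |
| 0.5 | 1.4–1.5 | 1.6–1.7 |
| 0.7 | 1.1–1.2 | 1.2–1.3 |

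The ratio also depends on the reference exposure. If that were 1.5 years, full exposure gives 1.9–2.0 at 3 years and 3.0–3.3 at 5 years.

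**4. Precision under unchanged hazard and full exposure.** The UTI margin is 1.96 × √(0.268 × 0.732/300) = 5.01 points at 3 years and 5.56 at 5 years. Zoster is 5.04 at 5 years. The other margins stay below 5.

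**5. Is 1.06 years the base of these percentages?** The two COMFORT trials randomised 309 + 219 = 528, fewer than 589. The ruxolitinib arms total about 300 to 301 (half of 309 plus two thirds of 219). No whole count out of 301 gives any of the five percentages. Counts of 38, 61, 3, 28 and 27 out of 589 give all five. Other denominators also fit all five, for example 413 to 415 and 433 to 434. A base of 589 is therefore plausible, not proven.

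**The case against.** A reader might infer that a doubling will appear whatever the risk. The documents do not support that. Three to five years is follow-up, and section 9.1.2 says it continues regardless of drug exposure. ADR collection ends 28 days after stopping, and section 9.7.4 speaks of on-treatment incidence. Patients also die: section 10 of the background discussion of prognosis in section 7 cites a median survival of 27 months in the high-risk group, which as an exponential illustration is ln 2/2.25 = 0.31 per year from death alone. At a loss rate of 0.3 per year the 3-year ratio is already below 2. This objection stands, and it limits the claim to what can happen.

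A reader might also take COMFORT for the only yardstick, or Table 9-1 for a signal rule. Neither holds. Section 9.1.2 says that non-exposed patients give context too, and section 9.7.7 is a sample-size justification with no formal test or decision threshold.

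The direction of bias is not fixed either. Some patients arrive already treated through earlier supply programs, and event capture here (ADRs, SAEs, events of special interest) may differ from the trials.

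Finally, incidence in section 9.7.4 need not mean a crude proportion. Treatment dates are collected (section 9.3.3), exposure duration is summarised (section 9.7.3), and patient-year rates may stand in an analysis plan not shown here. Their absence from the protocol is therefore no fault in itself. An analysis plan would not, however, supply the missing time basis of the figures fixed in section 9.7.7.

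**Conclusion.** The point holds in a limited form. The arithmetic in section 9.7.7 is correct; the flaw is that its benchmarks have no time basis and no named source population, in a study whose purpose is long-term safety. With an unchanged, roughly constant hazard and a 1.06-year reference, reaching the Table 9-1 rates takes only about 2.1 to 2.4 years on drug (4.3 for tuberculosis). A crude percentage above COMFORT, or twice it, would therefore not by itself show added risk. How far it exceeds COMFORT depends on persistence, which the protocol does not state.

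The precision claim is affected only marginally. It holds at the COMFORT rates and at Table 9-1's assumed rates, and fails by at most 0.56 points for UTI and 0.04 for zoster under full exposure.

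Severity: should-fix. Confidence: moderate, because the 1.06-year base is inferred and no decision rule depends on the comparison.

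**What to change.** In section 9.7.7, restate each benchmark as number of patients with a first event and patient-years at risk, or as a proportion at a common time point, and name the source population. Take these from the sponsor's trial data, not from the inferred 622/589. Recompute the precision statement and Table 9-1 on that basis, with the expected time on ruxolitinib stated.

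In sections 9.7.4 and 9.7.5, say that any review against the COMFORT profile will use exposure-adjusted incidence rates with 95% confidence intervals, or cumulative incidence at matched times, with crude percentages as supportive.

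The cost is protocol wording, some programming and retrieval of trial event and exposure data. No new data collection is needed, since treatment start and stop dates and event dates are already recorded. The drawback is that a patient-year rate assumes a roughly constant hazard within each interval, so rates should be shown by interval of time on drug where numbers allow.
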